Justification: Controlling homeostatic plasticity can reduce subject variability^{2;3} and the knowledge gained can be used to optimize rTMS treatment. What is needed to move the field forward is a method for combining tDCS and rTMS and for measuring neuronal responses directly which we aim to establish in this study. The long term goal of our work is to optimize rTMS as a treatment for tinnitus. The project will examine the targeted effects of neuromodulation in normal subjects and in patients with tinnitus. The brain regions targeted for intervention include auditory areas in the temporal cortex (TC) that process sounds and functionally connected regions of the dorsolateral frontal cortex (DLFC) that mediate sensory habituation. Further, we aim to determine how neuromodulation suppresses sound perception.

Objectives: One overall objective of this pilot study proposal is to determine how different activation states of the TC and DLFC (their homeostatic plasticity) interact with different doses of rTMS (1 Hz and 10 Hz) to produce LTD and whether these physiological changes can affect tinnitus-like behavior in normal subjects. Transcranial direct current stimulation (tDCS) will be used to modulate the activation states of TC and DLFC prior to rTMS. The primary outcome measure is change in cortical excitability, which will be measured *directly* from TC and DLFC using TMS evoked EEG potentials (TEPs). A 128 channel EEG recording cap with embedded high density tDCS electrodes was specifically designed by our research team to interleave TMS/EEG recording with tDCS and rTMS delivery. A second objective, is to investigate how

Study Title: Regulating homeostatic plasticity and the physiological response to rTMS
PI: [name]
Institution: University of Arkansas for Medical Sciences
Support: Department of Neurobiology and Dev. Scs.

tDCS preactivation of the DLFC prior to 1 Hz rTMS of the TC modifies cortical excitability (TEPs) and perception of tinnitus in a patient sample.

Hypothesis: Our central hypothesis for this pilot study is that increased cortical activation will facilitate the induction of LTD by rTMS, both at the treatment site in TC and in a network site in the DLFC. In patients with tinnitus, it is hypothesized that LTD induction will correlate with change in tinnitus perception.

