Study Title: Regulating homeostatic plasticity and the physiological response to rTMS
PI: [name]
Institution: University of Arkansas for Medical Sciences
Support: Department of Neurobiology and Dev. Scs.

conditions within each arm (Table 1). Subjects will be sequentially assigned to one of two parallel groups (1 Hz or 10 Hz rTMS).

Study endpoints: The primary outcome measure is the local mean field potential calculated for electrodes over the temporal and dorsolateral frontal cortex that are measured at baseline and after sham and active treatment conditions. An exploratory outcome measure is ratings of auditory stimuli detected by participants before and after each of the three experimental conditions.

Statistical Plan or Data Analysis: Aims 1 & 2 examine the effect of treatment dose on one primary outcome measure – a difference score between sham and active rTMS in the LMFP of TEPs (Δ LMFP) recorded from TC and DLFC. The analysis plan is the same for both aims. Hierarchical Linear Models (HLMs) will be used due to the nested structure of the design. HLMs will fit the complex covariance structure of the dosing schedule – sham and active tDCS nested within rTMS treatment frequency (1 Hz and 10 Hz).

Trial design, endpoints and analysis for Aim 3. The design is an open label, feasibility study – a pre-post examination of change in the LMFP of TEPs (Δ LMFP) recorded from TC and DLFC and in the ratings of tinnitus awareness, loudness and annoyance after four days of treatment. Aim 3 is conceptually similar to Aims 1 and 2 in using tDCS preconditioning of rTMS and in using EEG to evaluate change; however, treatment length and the timing and methods of assessing tinnitus were adopted from a previous study so that the data would be comparable.

What are the test articles TMS and tDCS?

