TMS/EEG is used in this proposal to measure the neural activity of targeted circuits. TMS/EEG is a method for probing superficial cortical brain regions to study intra-cortical neural circuits.¹⁹ During TMS/EEG, single (or paired) TMS pulses are delivered repeatedly to a region of the brain while the EEG is being recorded. The data in this proposal will be collected off line, before and after tDCS and rTMS, respectively. TMS evoked EEG potentials (TEPs) can be used to measure cortical excitation/inhibition directly from the cortex. TEPs have high test-retest reproducibility, particularly when stereotaxic systems are used to precisely control the location of TMS delivery from session-to-session.^{20;21} TEPs have been used in conjunction with MEPs to measure LTP induction in the motor cortex of healthy subjects.^{22;23} TEPs are particularly well suited for use in this proposal to assess cortical excitability in non-motor areas, like the TC and DLFC, as well as multiple other locations within and between the cerebral hemispheres. TEPs have the characteristics of a good biomarker of change in neural dynamics. They are easy to obtain, have high test-retest reproducibility, and they have been validated in studies of motor and frontal cortex.²⁰⁻²² TMS/EEG data can also provide information about the ability of stimulated brain regions to generate oscillations in discrete frequency bands of the EEG²⁴ and about the sources and propagation of neural activity in functionally connected brain regions²⁵ which will be examined in exploratory analyses.

Scientific Premise

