Study Design, Population, Apparatus and Investigational Plan

Aims 1 & 2.

Design: This is prospective, experimental design includes a block randomized, blinded, sham controlled, mixed effects model with sequential assignment to two treatment arms (1 or 10 Hz rTMS) and random assignment to three experimental conditions within each arm (Table 1).

Randomization: Subjects will be assigned sequentially to one of two parallel groups (1 Hz or 10 Hz rTMS: Table 1.5). Next, they will complete three experimental test sessions (Table 1). The order of test sessions is randomized. A minimum two week washout period will follow each session to minimize session to session carry forward effects.¹⁵ Washout can exceed two weeks.

[figure not shown]

Figure 1.5. Subject flow.

Study visits: Study visits will be to the transcranial magnetic stimulation laboratory, room 654-2, located on the 6th floor of the Biomedical II research building on the UAMS

Study Title: Regulating homeostatic plasticity and the physiological response to rTMS
 PI: [name]
 Institution: University of Arkansas for Medical Sciences
 Support: Department of Neurobiology and Dev. Scs.

campus. In total, there will be 4 study visits - 1 consent/screening visit and 3 laboratory visits per subject. The 3 laboratory study visits will be separated in time by a minimum of two weeks. The time required to complete a study visit ranges from 1 hour, when TMS/EEG is not collected, to 3.5 hours, when TMS/EEG is collected. TMS/EEG is recorded immediately before and after tDCS preconditioning, immediately following rTMS and after a 20-30-minute delay to examine the acute and lasting effects.

Subject flow: Twenty healthy subjects who meet the entry criteria and pass safety screening for tDCS and TMS will be enrolled (Figure 1.5). Ten subjects will be tested in each aim, with two parallel groups of 5 subjects receiving either 1 or 10 Hz rTMS. Two randomization lists of 10, each balanced between tDCS over TC and tDCS over DLFC, were generated based

on uniformly distributed random number generation in SAS v9.4. The first 10 recruited subjects will receive 1Hz rTMS treatment while the second 10 will receive

Experimental conditions & TMS/EEG assessments.								
Condition†	TMS/EEG	tDCS	TMS/EEG	rTMS	TMS/EEG	30 min delay	TMS/EEG	
1		sham		sham				
2		sham		active				
3		active		active				
Time (mins)	0	20	40	60	80	100	130	

Table 1. † The order of conditions is randomized. A 2 week washout separates each condition.

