Methods for TMS targeting. A template MRI scan will be uploaded into the Brainsight frameless stereotaxy system (Rouge Research, Montréal, Québec, Canada) and used to track stimulation delivery for all subjects. Brainsight uses 3D infrared tracking position sensors to reference the MRI to anatomical landmarks on the subject's head and to the TMS coil. Digitized markers can be placed on the MRI in Brainsight to ensure that the TMS coil is placed in the same locations from session to session. Brainsight will be used to target rTMS over the caudal two-thirds of the superior temporal gyrus (BA 22 in TC). During TEP recording, Brainsight will be used to target the TMS coil over BA 22 in the TC and to position the TMS coil over the convexity of the superior frontal gyrus where TEPs from the DLFC will be obtained. All stimulation sites will be marked in the Brainsight Stereotaxic system (RougeResearch) to ensure precise session to session targeting.

Methods for active and sham rTMS and study blinding. The MT will be established at the

Figure 5. Electrode location mock-up.

Study Title: Regulating homeostatic plasticity and the physiological response to rTMS
PI: [name]
Institution: University of Arkansas for Medical Sciences
Support: Department of Neurobiology and Dev. Scs.

beginning of each test session. A technician will set up equipment for each test session while the subject is being prepped for EEG recording, to keep them blind to condition. To check integrity of the blind, subjects will be asked to guess whether they received active or placebo stimulation at the end of each treatment session. Subjects are not providing subjective responses to intervention, which minimizes the possibility of experimenter bias. Persons who process EEG data for analysis and the biostatistician will be kept blind to condition using session codes. These procedures were used successfully in previous studies.⁴⁵

Aim 3.

The methods for tDCS preconditioning in Aim 3 is identical to that described for Aims 1 and 2 except that the high density stimulating electrodes will be placed in a cap specifically designed by the manufacture rather than the 128 channel EEG recording cap (as in Aims 1 & 2). Additionally, only active tDCS will be delivered.

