Data collection will be accomplished via case report forms and electronic recording via the devices used in this study. The Principal Investigator will carefully monitor study procedures to protect the safety of research subjects, the quality of the data and the integrity of the study. Participant's data will be de-identified using codes, personal identifiers will be kept separate from study data, and data will be locked in file cabinets or drawers in the TMS laboratory and in the PI's office, if hardcopy, or on a password-protected UAMS server, both located behind locked doors in a restricted access area of the UAMS campus. Only authorized individuals will have access to the code and information that identifies the subjects in this study. Following informed consent to participate, patient's hospital and outpatient records may be reviewed to identify appropriate candidates for the study. Any data obtained as part of the patient's clinical care may be reviewed to determine whether the subject meets inclusion and does not meet exclusion criteria.

Data Analysis

Analyses and Power calculations.

Aims 1 & 2 examine the effect of treatment dose on one primary outcome measure – a difference score between sham and active rTMS in the LMFP of TEPs (Δ LMFP) recorded from TC and DLFC. The analysis plan is the same for both aims. Hierarchical Linear Models (HLMs) will be used due to the nested structure of the design. HLMs will fit the complex covariance structure of the dosing schedule – sham and active tDCS nested within rTMS treatment frequency (1 Hz and 10 Hz). Four primary responses will be estimated, namely Δ LMFP for the sham vs active tDCS and the 1 Hz vs 10 Hz rTMS conditions. From these four responses, four contrasts of interest will be estimated: (1) sham vs active tDCS for 1 Hz rTMS, (2) sham vs active tDCS for 10 Hz rTMS, (3) 1 Hz vs 10 Hz rTMS for sham tDCS, and (4) 1 Hz vs 10 Hz rTMS for active tDCS. An additional 6 contrasts will be used to examine differences in the means for the rTMS post 1 (acute) and post 2 (lasting) time periods. The HLM methodology will estimate the means and standard errors for all these contrasts of interest with a Bonferroni comparison procedure to adjust for the multiple contrasts.

Power Estimates

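### Aims 1 and 2: the ΔLMFP analysis gives the pre-tDCS TEP of each session no stated role; a same-region session baseline covariate in one pooled model is a cheap, though not assured, gain in precision

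*Combined protocol and SAP*

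**What the plan says.** The section Analyses and Power calculations gives one primary outcome for Aims 1 and 2, ΔLMFP, described as "a difference score between sham and active rTMS in the LMFP of TEPs" and recorded from TC and DLFC. It is fitted by hierarchical linear models with four contrasts of interest. "An additional 6 contrasts will be used to examine differences in the means" for the acute and lasting periods, and all are estimated "with a Bonferroni comparison procedure to adjust for the multiple contrasts". No covariate is named.

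Table 1 places sham/sham, sham/active and active/active (tDCS/rTMS) in three separate sessions in randomized order, at least two weeks apart. Under Study visits: "TMS/EEG is recorded immediately before and after tDCS preconditioning, immediately following rTMS and after a 20-30-minute delay". So each session has its own recording before any stimulation.

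Two parts of the Protocol Summary point towards a baseline. Objectives says "The primary outcome measure is change in cortical excitability", and Study endpoints says LMFP is "measured at baseline and after sham and active treatment conditions". Neither says whether the baseline is subtracted, adjusted for or only described. Explicit change from baseline is specified only for Aim 3.

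**The concern.** Two analysts could compute different primary outcomes from the same recordings: (a) post-rTMS LMFP compared between sessions, or (b) within-session change compared between sessions. Reading (a) leaves all session-to-session noise in the contrasts. Reading (b) adds the noise of the baseline recording and forces a baseline slope of 1. A covariate estimates that slope instead.

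The contrasts rest on very few sessions. Each subject has one sham-rTMS session, so contrasts 1 and 2 reduce to (active/active − sham/sham) − (sham/active − sham/sham) = active/active − sham/active. That is a two-session difference in 5 subjects. Contrasts 3 and 4 compare two-session differences between two arms of 5.

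The protocol's Scientific Premise names unknown baseline excitability as a source of variable rTMS response and proposes TEPs to measure it. The analysis then does not say how that measurement is used.

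**Working it through.** **The plan's own figure.** The documents give no precision figure for ΔLMFP, only MEP-based power from two-sample t-tests with n = 5. I assumed two-sided alpha 0.05. For 1 Hz acute, effect size 2.95 gives 98.2%, and (0.89 − 0.64)/0.08 = 3.125 gives 99.0%; the plan says 99%. The 30-minute 1 Hz entry does not reproduce: 0.95 gives 26%, and the printed 48% needs about 1.37. Nothing below depends on that entry.

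**Inputs.** From the documents: 2 arms of 5 per aim and 3 sessions per subject. Assumed: r between 0 and 0.9, equal pre and post variance, normal errors and one common slope.

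**Degrees of freedom per aim.** 30 session values − 10 subject effects − 4 within-arm condition differences = 16, or 14 after two period terms. The covariate takes one more.

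**Formulas**, with ν the residual df before the covariate:
- change score / post-only, variance: 2(1 − r)
- covariate / post-only, variance: (1 − r²)(1 + 1/(ν − 2))
- covariate / change score, variance: [(1 + r)/2](1 + 1/(ν − 2))
- CI width ratio: square root of the variance ratio × t(ν − 1)/t(ν)

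With ν = 14 the slope-estimation factor is 1 + 1/12 = 1.083 and the 95% t ratio is 2.160/2.145 = 1.007.

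| r | Change / post-only, variance | Covariate / post-only, variance | Covariate / post-only, CI width | Covariate / change, CI width |
|---|---|---|---|---|
| 0 | 2.0 | 1.08 | 1.05 | 0.74 |
| 0.2 | 1.6 | 1.04 | 1.03 | 0.81 |
| 0.3 | 1.4 | 0.99 | 1.00 | 0.85 |
| 0.5 | 1.0 | 0.81 | 0.91 | 0.91 |
| 0.7 | 0.6 | 0.55 | 0.75 | 0.97 |
| 0.9 | 0.2 | 0.21 | 0.46 | 1.02 |

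Without period terms (ν = 16) the factor is 1 + 1/14 = 1.071, so the r = 0 cost is 7% in variance and about 4% in CI width. Simulation of 10 subjects × 3 sessions agrees with and without period terms.

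**Break-even.** With period terms, the covariate narrows the 95% interval against post-only above r of about 0.30 and against change below about 0.82. In variance terms without period terms, the limits are sqrt(1 − 1/1.071) = 0.26 and 2/1.071 − 1 = 0.87.

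**Slopes that differ by condition.** Assumed slopes for sham/sham, sham/active and active/active, no period terms, contrast 1 variance relative to post-only by simulation: 0.7/0.3/0 gives 1.06, 0.9/0/0 gives 1.15, and 0.9/0/−0.5 gives 1.18. At 0.9/0/0 the model's own interval does not widen (ratio 0.99), so it overstates precision there. The covariate still beats the change score in these cases.

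**Arms modelled separately.** Three sessions in one arm, with period effects: CI ratio 1.14 against post-only at r = 0, and 1.12 against change at r = 0.9. Five paired differences alone (df 4 to 3): (3.182/2.776) × sqrt(1.5) = 1.40 against post-only at r = 0.

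**Power, for scale.** Bonferroni over 4 + 6 = 10 contrasts gives 0.05/10 = 0.005. Contrast 1, pooled model without period terms, effect in session SDs (carrying an MEP effect size over to LMFP is an assumption):

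| Effect | Post-only | Covariate, r = 0.3 | r = 0.5 | r = 0.7 | r = 0.9 |
|---|---|---|---|---|---|
| 0.95 | 7% | 7% | 9% | 14% | 54% |
| 1.37 | 18% | 18% | 25% | 40% | 91% |

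At 2.95, post-only already has about 90%, against 90% at r = 0.3 and 95% at r = 0.5.

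**The case against.** The strongest reply is that r is unknown. The plan says "TEPs have high test-retest reproducibility, particularly when stereotaxic systems are used to precisely control the location of TMS delivery from session-to-session" and uses stereotaxic tracking "to ensure that the TMS coil is placed in the same locations from session to session". A reader might infer from this that r is high and the gain large. The documents do not support that. Stable differences between subjects already cancel in within-subject contrasts, and high reproducibility could leave little session-level signal for a baseline to explain. No coefficient is given, and Power Estimates says TEP data for a power analysis do not yet exist. This objection stands: the gain is possible, not assured.

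Second, the protocol's own theory questions a shared slope. If prior activity decides whether rTMS excites or inhibits, the relation of baseline to post-rTMS LMFP may differ by condition. This also stands; it is why the loss can exceed 7-8% and why an unadjusted sensitivity analysis is needed.

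Third, the larger losses arise when arms are analysed alone. The plan's model covers both frequencies, so pooling fits it, but the plan does not specify a shared slope. The low cost depends on stating one.

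Fourth, baseline is not absent from the plan, since Study endpoints mentions it. That is correct. The gap is that the analysis does not say how baseline enters.

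**Conclusion.** The analysis text leaves a recording made in every Aim 1 and 2 session unused and does not settle whether post-rTMS values or changes are compared. A session-level baseline covariate is the sounder default because its loss is small under the pooled model and its possible gain is large.

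With a common slope, equal variances and both arms pooled, the cost is 1 df. Against post-only at r = 0 that means at most about 7-8% more variance, or a CI about 4-5% wider. Against the change score at r = 0.9 the CI is about 2% wider. At r = 0.5 the CI is about 10% narrower than under either reading. At the extremes the gain is larger: about 26% narrower than change at r = 0, and about 54% narrower than post-only at r = 0.9. The loss against post-only can reach about 15-18% in variance if slopes differ strongly by condition.

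A reader might infer that adjustment helps under either reading at any r, that the current plan is biased, or that adjustment would repair low power. None of these follows. There are break-even points in both directions; condition order is randomized, so this is a matter of precision; and at modest r and modest effects power hardly moves. The point is worth considering in a pilot and is not a defect that invalidates it.

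**What to change.** In Analyses and Power calculations, define the Aim 1 and 2 outcome as each session's post-rTMS LMFP for a named region (TC or DLFC). For each region, fit one model per aim that pools the 1 Hz and 10 Hz arms and includes period terms. Adjust for the same region's pre-tDCS LMFP, split into the subject's mean and the session's deviation from it, with one slope for the deviation shared across arms and conditions. The split keeps between-subject differences from being mixed into the session-level slope.

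Use only the recording made before tDCS; the post-tDCS TEP may already reflect treatment. Report a sensitivity analysis without the covariate. Report the estimated slope or correlation with its interval, since the pilot is meant to supply data for sizing the next study.

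The cost is wording and one within-subject degree of freedom (14 to 13 per aim with period terms). No visit or recording is added. Validity relies on the two-week washout being long enough that the previous session does not alter the next baseline.

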Specific Aim 1: Determine in normal healthy subjects how increased activation of the TC modifies the induction of LTD by 1 Hz and 10 Hz rTMS. Analyses will examine difference scores between sham and active rTMS in the local mean field power (LMFP) of TEPs (Δ LMFP) recorded from TC and DLFC. Parallel groups of healthy subjects (n=5 each) will receive 1 and 10 Hz rTMS. Four contrasts are of interest – (1) sham vs active tDCS for 1 Hz rTMS, (2) sham vs active tDCS for 10 Hz rTMS, (3) 1 Hz vs 10 Hz rTMS for sham tDCS, and (4) 1 Hz vs 10 Hz rTMS for active tDCS. Our working hypothesis is that increased cortical activation will facilitate LTD following rTMS at both frequencies of stimulation, but the effect for 1Hz will be stronger for than for 10 Hz.

Specific Aim 2: Determine in normal healthy subjects how increased activation of the DLFC modifies LTD induced by 1 Hz and 10 Hz rTMS over the TC. New groups of subjects will be recruited. The design, analyses, and predictions are the same as for Aim 1. The difference is that circuits in the DLFC, a functionally connected network, are being preconditioned rather than TC. We predict that rTMS delivered to the TC will induce LTD in the DLFC after it has been preconditioned with tDCS.

Exploratory Aim. We will develop and test a behavioral model of sound perception in healthy participants who have normal hearing by placing them in a sound attenuated environment and measuring ratings of sounds played above threshold. We will examine how tDCS/rTMS modify these perceptions.

Specific Aim 3: Determine in patient with tinnitus how increased activation of the DLFC modifies LTD and tinnitus perception induced by 1 Hz rTMS over the TC. We will recruit ten subjects from a previous study of rTMS for tinnitus (109033) who agreed to be contacted for future research projects. We will examine change from baseline in TEPs (Δ LMFP) recorded from TC and DLFC and on ratings of tinnitus awareness, annoyance and loudness following three days of treatment (tDCS preconditioning of the DLFC followed by 1 Hz rTMS of the TC). Analyses will examine change from baseline for TEPs and tinnitus ratings. Change scores for tinnitus ratings will be compared to those for sham and active rTMS treatments from a previous study (109033).

Aims 1 & 2 Design: A randomized, blinded, sham controlled, mixed effects model with assignment to two treatment arms (1 or 10 Hz rTMS) and three experimental

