One purpose of the pilot study is to collect TEP data for a power analysis because such data does not currently exist. To estimate power for the pilot study, effect sizes for the contrasts of interest in Aims 1 and 2 were estimated from the means and SDs of MEP amplitudes in two published studies that used anodal, 1 mA tDCS to precondition the motor cortex before rTMS was delivered a 1 Hz²⁸ or 5 Hz³ (power estimates for 10 Hz stimulation were based on the 5 Hz study). As in our design, change in cortical

Study Title: Regulating homeostatic plasticity and the physiological response to rTMS
PI: [name]
Institution: University of Arkansas for Medical Sciences
Support: Department of Neurobiology and Dev. Scs.

excitability was measured both immediately following rTMS (acute) and 30 minutes later (lasting effects). PASS 12 was used to calculate power by estimating power, conservatively, as two-sample t-tests (n=5 for all comparisons). For 1 Hz TMS, the power to detect a difference in MEP amplitude between the sham (mean=.89, SD=.08) and active (.64; .08) tDCS conditions was 99% acutely (effect size=2.95) and 48% at 30 minutes (effect size=95%). For the 5 Hz condition, power to detect a difference in MEP amplitude between sham (.99; .16) and active (.98; .16) tDCS was only 6% acutely (effect size=.06) but 100% at 30 minutes (effect size=4.80). Finally, the power to detect a difference in MEP amplitude between 1Hz (.64; .08) and 10Hz (.98; .16) rTMS (after active tDCS preconditioning) was 94% acutely (effect size=2.68) but only 8% at 30 minutes (effect size=.39). Importantly, anodal preconditioning induced LTD (a decrease in the MEP amplitude) in both the 1 and 5 Hz conditions but, consistent with the hypothesis for Aims 1 & 2, the effect was stronger for 1 Hz than 5 Hz rTMS. These estimates give confidence that the sample sizes of our pilot study are sufficient to test Aims 1 & 2.

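### A flat Bonferroni adjustment over what appear to be ten contrasts is valid but costs the four Aim 1 and 2 contrasts power that Holm with an ordered family would recover

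*Combined protocol and SAP*

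**What the plan says.** Specific Aim 1 in the Protocol Summary states that "Four contrasts are of interest": sham against active tDCS at 1 Hz (contrast 1) and at 10 Hz (contrast 2), and 1 Hz against 10 Hz after sham tDCS (contrast 3) and after active tDCS (contrast 4). Aim 2 takes over the same design and analysis.

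Analyses and Power calculations, under Data Analysis, repeats this: "From these four responses, four contrasts of interest will be estimated". It continues: "An additional 6 contrasts will be used to examine differences in the means", here for the acute (post 1) and lasting (post 2) periods after rTMS. The hierarchical model is then to give the "means and standard errors for all these contrasts of interest" "with a Bonferroni comparison procedure to adjust for the multiple contrasts".

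The section does not list the six contrasts, rank them below the four, or state the divisor, overall alpha or sidedness. It does not say at which time point the four are tested, or whether the two regions (TC and DLFC) and the two aims count in the family.

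Power Estimates computes power as "two-sample t-tests (n=5 for all comparisons") and mentions no multiplicity adjustment.

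**The concern.** The phrase about all these contrasts follows directly on both lists, so the most natural family is 4 + 6 = 10. Under flat Bonferroni each contrast gets one tenth of alpha whatever its place in the aims. With five subjects per group and 8 degrees of freedom, the critical t value rises steeply as alpha falls, so the divisor matters.

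Two things are at stake. First, the four contrasts that define Aims 1 and 2 lose power that another procedure with the same family-wise error rate would keep. Second, the stated power, and the conclusion drawn from it that the sample sizes suffice for Aims 1 and 2, do not describe the adjusted tests that will be run.

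**Working it through.** **Inputs.** All are from Power Estimates: n = 5 per group and a two-sample t-test, so 8 df. Contrast 1, acute, compares "sham (mean=.89, SD=.08) and active (.64; .08) tDCS conditions", with printed effect size d = 2.95; power "was 99% acutely (effect size=2.95) and 48% at 30 minutes (effect size=95"%). The last figure is read here as d = 0.95. Contrast 2 has d = 0.06 (acute) and 4.80 (30 minutes), with 5 Hz data standing in for 10 Hz. Contrast 4 has d = 2.68 and 0.39. No power is given for contrast 3. Overall alpha is assumed to be 0.05 two-sided, the setting under which most of the printed powers reproduce.

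**Formula.** Power = P(|T| > t_crit), where T is noncentral t with 8 df and noncentrality d × √(5/2). For d = 2.95 this is 4.66; for d = 2.68 it is 4.24.

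**Reproducing the plan at unadjusted 0.05 (t_crit = 2.306).**

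| Contrast | d | Stated | Recomputed |
|---|---|---|---|
| 1, acute | 2.95 | 99% | 98.2% |
| 1, 30 min | 0.95 | 48% | 26.3% |
| 2, acute | 0.06 | 6% | 5.1% |
| 2, 30 min | 4.80 | 100% | 100% |
| 4, acute | 2.68 | 94% | 95.8% |
| 4, 30 min | 0.39 | 8% | 8.5% |

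The printed means and SDs for contrast 1 give d = (0.89 − 0.64)/0.08 = 3.125 and 99.0%. An unequal-variance (Welch) test for contrast 4 gives 93.8%. So five of the six figures reproduce within 2 points, with no multiplicity adjustment. The 48% does not follow from d = 0.95; it would need d of about 1.37.

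**Power at the adjusted levels.** The critical t is 3.206 at 0.05/4 = 0.0125 and 3.833 at 0.05/10 = 0.005.

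| Contrast | 0.05 | 0.05/4 | 0.05/10 |
|---|---|---|---|
| 1, acute (d = 2.95) | 98.2% | 88.8% | 75.7% |
| 4, acute (d = 2.68) | 95.8% | 81.3% | 65.3% |
| 4, acute, Welch | 93.8% | 72.9% | 52.8% |
| 1, 30 min (d = 0.95) | 26.3% | 10.3% | 5.1% |
| 2, 30 min (d = 4.80) | 100% | 99.97% | 99.7% |

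Going from 0.05/4 to 0.05/10 costs 88.8 − 75.7 = 13.1 points for contrast 1 and 81.3 − 65.3 = 16.0 points for contrast 4, both acute. Contrast 1 is within subject; as a paired test (4 df, correlation 0.5 assumed) it has 91.8% against 74.0%. The d needed for 80% power rises from about 2.65 to 3.08.

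**Sensitivity to the undefined family.** Four contrasts in two regions make 8 tests: at 0.05/8, contrasts 1 and 4 (acute) have 79.4% and 69.5%. Adding two time points makes 16: at 0.05/16 they have 67.3% and 56.1%. The 0.05/4 column therefore presupposes one region and one time point.

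**Error rate over all ten contrasts.**

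- Flat Bonferroni: bound 10 × 0.005 = 5%.
- Four at 0.0125 and six read as tests at unadjusted 0.05: bound 4 × 0.0125 + 6 × 0.05 = 35%; if independent, 1 − 0.9875⁴ × 0.95⁶ = 30.1%.
- Four at 0.0125, with each rejection passing its 0.0125 to the six jointly: simulated at about 4.9% with every null true (independent tests).

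**The case against.** The strongest reply is that nothing here is invalid. Flat Bonferroni holds the family-wise error at or below 5% for all ten contrasts and yields simple simultaneous intervals, which suit a pilot meant partly to supply data for later power calculations. That stands, and it limits the point to efficiency.

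A reader might go further and infer that including the six timing contrasts buys no error control. It does: it protects those six. Dropping the adjustment for them while still reading them as tests would let the error rate over the ten reach 30% to 35%.

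A reader might also call the six secondary. The plan says only additional, and Study visits schedules the repeat recordings in order to study acute and lasting effects, so treating them as inferential is a legitimate choice.

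Nor can six be shown to be a miscount. Comparing the two periods within each of the four responses gives four contrasts, and three conditions by two frequencies gives six; but four means also have six pairwise differences. The documents support only the statement that the six are not listed.

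Finally, the divisor does not matter everywhere. Contrast 1 at 30 minutes is poorly powered at either level, and contrast 2 at 30 minutes is nearly certain at either. The loss falls on the acute contrasts 1 and 4.

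**Conclusion.** The point holds as one of efficiency and definition. On the natural reading of ten contrasts, flat Bonferroni is valid but takes about 13 and 16 points of power from the acute contrasts 1 and 4, compared with testing the four first at 0.05/4. Against the unadjusted level behind the printed powers, contrast 1 falls from 98% to 76% and contrast 4 from 96% to 65%, so the claim of sufficient sample size is not supported at the planned adjustment. It does not follow that the pilot is too small for its purpose, since it is also meant to gather TEP data that did not exist.

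The figures rest on an overall two-sided alpha of 0.05, a family of ten, one region and one time point, and the plan's effect sizes, which come from motor evoked potentials in published studies rather than from TEPs. Because this is a pilot, the consequence is confined to how the tests may be interpreted.

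**What to change.** In Analyses and Power calculations:

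1. State overall alpha and sidedness, fix the region and time point of the four contrasts in advance, and list the timing contrasts one by one.
2. Within each aim, test the four contrasts first by Holm's step-down procedure. Holm controls the same family-wise error as Bonferroni under any dependence and rejects everything Bonferroni rejects, so it is never less powerful. State that control is per aim: over both aims the bound is 2 × 5% = 10%.
3. Test the timing contrasts only with alpha passed on from rejected primary contrasts. If Holm is used in full on the four, alpha reaches the six only when all four are rejected. That could be rare: the plan gives contrast 2 just 6% acutely, even unadjusted. If partial passing is wanted, test the four at 0.0125 each and let each rejection release its share to the six. The choice must be written down, because the same alpha cannot be used both ways. If no confirmatory timing claim is intended, report the six as descriptive with unadjusted intervals.
4. Under Power Estimates, restate power at the adjusted alpha and correct or explain the 48%.

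The cost is a few sentences, with no change to conduct. Holm gives no simple simultaneous intervals, though Bonferroni intervals can be shown alongside, and the timing contrasts become conditional or descriptive.
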